Chronic graft-versus-host-disease (GVHD) is a major complication of allogeneic hematopoietic cell transplant that impairs quality of life, and is associated with significant morbidity and mortality. Management of chronic GVHD with prednisone is associated with an overall response rate of approximately 60%, and a complete response rate of approximately 30% but sclerotic features do not respond as well. Based on the biology of chronic GVHD and available preliminary evidence, we hypothesize that ruxolitinib will be effective in the management of sclerotic chronic GVHD. The study is an open label, phase II multicenter trial designed to evaluate the efficacy of ruxolitinib as a salvage treatment for subjects with sclerotic GVHD (sclerosis or fasciitis). The primary objective is to determine the proportion of subjects with response rate (complete and partial responses) in skin and/or joint, as determined by 2014 NIH consensus criteria, at 6 months of therapy with ruxolitinib. Eligibility criteria includes adult subjects with chronic GVHD and skin, joint and/or fascia sclerosis, who have received systemic corticosteroids for >12 months and at least one additional line of therapy OR systemic corticosteroids and at least two additional lines of therapy for chronic GVHD. A sample size of 47 subjects dosed (42 evaluable subjects and estimated 10% dropout) will allow an α of 0.044 and a power of 84% to test the null hypothesis response rate of 25% compared to an alternative of 45%. Subjects will receive ruxolitinib for 6 months for the treatment of sclerotic chronic GVHD. Subjects will be evaluated for GVHD status as well as non-relapse mortality, relapse of underlying malignancy and quality of life/functional status. Plasma cytokine levels and T/NK cell subset in peripheral blood will be measured at various time points. The response rate will be reported as a proportion and 95% exact confidence interval. If positive, the trial results will support other ongoing studies to establish the role of ruxolitinib in chronic GVHD in general and specifically in sclerotic chronic GVHD.

Study Schema

Patients with chronic graft-versus-host-disease and skin, joint and/or fascia sclerosis, who have received systemic corticosteroids for >12 months and at least one additional line of therapy OR systemic corticosteroids and at least two additional lines of therapy

Informed consent and registration

Ruxolitinib therapy for 6 months

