10.1 Study Design and Sample Size Description

The study is an open label, phase II, multicenter trial designed to evaluate ruxolitinib as a salvage treatment for subjects with sclerotic GVHD (sclerosis or fasciitis).

If a subject receives one dose of ruxolitinib then the subject will be included in the safety analysis set.

The full analysis set will include all subjects that are evaluable at 6 months as well as subjects who are considered a treatment failure (including deaths) prior to 6 months. Subjects who drop out of the study prior to 6 months for reasons unrelated to treatment will be excluded from the full analysis set.

The primary endpoint is complete and partial responses in skin and/or joint, as determined by 2014 NIH Criteria (1) at 6 months from initiation of ruxolitinib without addition of any other systemic chronic GVHD treatment, relapse of the underlying disease, or death. The historical benchmark for overall response for steroid refractory sclerotic chronic GVHD is 25% in a randomized phase II trial by Arai et al., comparing imatinib and rituximab (15). In the trial by Arai et al., a significant clinical response was defined as “2 or more point improvement on the Vienna Skin Score without worsening elsewhere or at least a 1-point improvement in the 4-level P-ROM scale or a 2-point improvement in the 7-level scale without worsening elsewhere.” The Vienna Skin Score is different from the 2014 NIH criteria (1) for responses in skin and/or joint. According to the 2014 NIH guidelines (1), “because the NIH 0 to 3 Skin Score is now recommended for response assessment, even substantial improvement in sclerotic features will not be considered responses unless the NIH Skin Score improves.” For this reason, for the purpose of the stopping rules, responses will include complete and partial responses in skin and/or joint, at least a 2-point improvement on 0-10 semiquantitative scale for capturing clinician-perceived severity of sclerosis, or clinically significant improvement (improvement by ≥ 6 point) on the skin subscale of the Lee symptom scale, consistent with the recommendations of the 2014 NIH Criteria (1). Additionally, improvement in percentage of BSA involved with deep sclerosis/fasciitis will also be taken into consideration as a marker of responses.

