A two-stage design is planned to test the null hypothesis that the overall response rate $p \leq 0.250$ versus the alternative that $p \geq 0.450$. The first stage will occur once 18 subjects have completed 6 months of treatment. If only 4 or fewer out of the 18 subjects respond at the end of 6 months of treatment, the trial will be stopped for futility. At stage two, an additional 24 subjects will be enrolled for a combined total of 42 from both stages. If only 15 or fewer respond out of 42 subjects at the end of stage two, then no further investigation is warranted. If 16 or more respond then further investigation is warranted. This design achieves 84% power with a significance level of 0.044. Retrospective studies (31, 32, 40) have demonstrated that ruxolitinib is well tolerated and effective in patients with steroid-refractory chronic graft-versus-host disease (GVHD) in general and sclerotic GVHD. Therefore, the accrual will not be put on hold for interim analysis.

To meet our statistical endpoints, a sample size of 42 is required; however, to account for dropout rate of approximately 10%, the study will dose 47 subjects.

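### The stated significance level of 0.044 does not follow from the two-stage rule, whose exact type I error is 0.040 with 42 analysed and one response definition throughout

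*Combined protocol and SAP*

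**What the plan says.** Section 10.1 defines the design completely. The null hypothesis is a response rate of at most 0.25 and the alternative a rate of at least 0.45. Stage 1 has 18 subjects, with a futility stop: "If only 4 or fewer out of the 18 subjects respond at the end of 6 months of treatment". Stage 2 adds 24 subjects, for a total of 42. The trial is negative as follows: "If only 15 or fewer respond out of 42 subjects at the end of stage two". On the other side: "If 16 or more respond then further investigation is warranted". The operating characteristics follow: "This design achieves 84% power with a significance level of 0.044". The synopsis prints the same pair, with 42 evaluable subjects: "an α of 0.044 and a power of 84% to test the null hypothesis response rate of 25" per cent.

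Three other statements in Section 10.1 limit what any single alpha can cover:

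- The response definition is widened for the interim decision: "for the purpose of the stopping rules, responses will include complete and partial responses in skin and/or joint", together with improvement on a clinician severity scale or on the skin subscale of the Lee symptom scale.
- The analysed number is not fixed in advance: "The full analysis set will include all subjects that are evaluable at 6 months", plus subjects who count as treatment failures before then.
- More than 42 are to be treated: "to account for dropout rate of approximately 10%, the study will dose 47 subjects".

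Neither place gives a derivation, software or convention for 0.044.

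**The concern.** A two-stage rule with fixed counts has one exact type I error and one exact power at given response rates. Both can be computed from the figures in Section 10.1. If the power reproduces and the alpha does not, the rule has been read as intended and the printed alpha is wrong for it.

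Alpha is a headline design figure, given to three decimals in two places, and a reader who checks it will not recover it. The stake is accuracy of reporting. The decision compares counts with 4 of 18 and 16 of 42, and no p-value is compared with 0.044, so the discrepancy does not alter the conduct or outcome of the trial.

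**Working it through.** **Inputs** (Section 10.1; the synopsis agrees on the rates and the total): null rate 0.25; alternative 0.45; stage 1 size 18, continue if 5 or more respond; stage 2 size 24; success if the total is 16 or more of 42.

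**Formula.** With X1 ~ Bin(18, p) and X2 ~ Bin(24, p) independent,

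P(success | p) = Σ over x = 5,…,18 of P(X1 = x) × P(X2 ≥ 16 − x).

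This assumes exactly 42 analysed and the same response definition at both stages.

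**Power at p = 0.45.** The sum is 0.8406, which reproduces the stated 84%. The probability of stopping at stage 1 is P(X1 ≤ 4) = 0.041.

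**Type I error at p = 0.25.** The probability of stopping at stage 1 is 0.519. The terms are:

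| x | P(X1 = x) | P(X2 ≥ 16 − x) | product |
|---|---|---|---|
| 5 | 0.1988 | 0.0213 | 0.00424 |
| 6 | 0.1436 | 0.0547 | 0.00785 |
| 7 | 0.0820 | 0.1213 | 0.00995 |
| 8 | 0.0376 | 0.2338 | 0.00879 |
| 9 | 0.0139 | 0.3926 | 0.00547 |
| 10 | 0.0042 | 0.5778 | 0.00241 |
| 11 | 0.0010 | 0.7534 | 0.00076 |
| 12 | 0.0002 | 0.8850 | 0.00017 |
| 13–18 | | | 0.00003 |

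The unrounded sum is 0.0397, or 0.040 to three decimals. A simulation of 4 million trials gave 0.0396. The difference from the stated figure is 0.044 − 0.0397 = 0.0043, too large to be rounding.

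**Could the interim rule explain 0.044?** A futility stop can only remove successes, so the highest alpha available with 16 of 42 is the single-stage value P(X ≥ 16 | 42, 0.25) = 0.0416. A search over every stage 1 size and futility bound with this final rule found nothing higher.

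The same ceiling covers a split in the response definition. Suppose the wider definition decides stage 1 and the NIH endpoint decides the final count in 42 subjects. Success still requires 16 NIH responses among 42, so alpha is at most 0.0416.

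**Could a misprinted final cut-off explain it?** With the same stage 1 rule and 42 analysed:

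| Success if at least | alpha (0.25) | power (0.45) |
|---|---|---|
| 15 | 0.0745 | 0.895 |
| 16 | 0.0397 | 0.841 |
| 17 | 0.0192 | 0.762 |

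Neither neighbour gives 0.044, and both lose the 84% power.

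**Could an approximation explain it?** For 16 of 42, the normal approximation gives 0.0250 uncorrected and 0.0374 with continuity correction. The Poisson approximation gives 0.0683, and doubling the exact value for two sides gives 0.0794. None is 0.044.

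**Dependence on the number analysed.** Keeping 4 of 18 and a final cut-off of 16, alpha at p = 0.25 is:

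| Analysed | 41 | 42 | 43 | 44 | 47 |
|---|---|---|---|---|---|
| alpha | 0.0321 | 0.0397 | 0.0484 | 0.0582 | 0.0940 |

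The stated 0.044 lies between the values for 42 and 43 and matches neither. The dropout allowance itself reproduces: 42/(1 − 0.10) = 46.7, rounded up to 47.

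**The case against.** The strongest reply is that nothing depends on the number. The gap is 0.0043, both values are below 0.05, and with 42 analysed the plan overstates its error. Decisions use counts, and Section 10.2.1 reports a proportion with an exact 95% interval, so 0.044 enters no analysis. All of that stands, and it is why the point is minor.

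A second reply is that the synopsis wording could mean a level not to be exceeded, which the rule does satisfy. Section 10.1, however, presents the figure as what the design attains, beside a power quoted at its attained value. The softer reading does not explain where 0.044 came from.

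A third is that 0.044 might belong to a different design, with the counts being the wrong part. Such designs exist: stopping at 6 or fewer of 21, then requiring 16 or more of 43, gives alpha 0.0435 and power 0.836. But that contradicts the counts in Section 10.1, which agree with one another (18 + 24 = 42) and reproduce the stated power. The documents do not show the origin of 0.044, so a look at the source calculation is sensible, but the figure is wrong for the rule as written.

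Finally, quoting alpha at the planned size is normal practice, and 42 already appears near the figure in both places. What to do when the analysed number is not 42, and which response definition applies at which stage, are separate questions. They are used here only to mark the limits of the corrected figure and do not raise its severity.

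**Conclusion.** The concern holds and is minor. For exactly 42 analysed subjects, a null rate of 0.25 and one response definition at both stages, the rule has an exact type I error of 0.0397 against the stated 0.044. If the wider definition governs stage 1 only and the NIH endpoint governs the final count, the error is at most 0.0416. The stated 84% power is correct at 0.8406. Under these conditions the discrepancy is in the conservative direction. No conclusion is drawn for other readings of the response definition. With other analysed totals the error differs, and with the cut-off kept at 16 it exceeds 0.05 from 44 analysed.

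**What to change.** In the synopsis and in Section 10.1, replace 0.044 with 0.040 and state its basis: exact binomial, null rate 0.25, 42 analysed. If the wider response definition is meant to apply at stage 1 only, write instead that the level is at most 0.042 with 42 analysed. Keep the condition of 42 attached to the figure, because 47 are to be dosed and the figure holds for 42 only. The source calculation should be checked when the change is made. The cost is one number and its condition in two places; sample size, cut-offs and power stay as they are.

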10.2 Analysis plan

Descriptive statistics will be computed for subject characteristics. Mean, standard deviation (SD), median and range will be reported for continuous variables and frequencies and percentages will be used to describe categorical variables.

10.2.1 Efficacy Endpoints

Primary and secondary objectives

The primary objective of the study is to determine the complete and partial responses in skin and/or joint after 6 months of therapy. The response rate will be reported as a proportion and 95% exact confidence interval. This analysis will be conducted on the full analysis set.

The secondary objective is to determine the overall complete and partial responses after 6 months of therapy. The response rate will be reported as a proportion and 95% exact confidence interval.

Exploratory Objectives

Treatment failure (treatment failure defined as: administration of additional systemic therapy for chronic GVHD, malignancy relapse or mortality) by 6 months from study enrollment.

Time to treatment failure will be defined as study enrollment to failure event. Kaplan-Meier methods will be used to estimate the distribution for time to treatment failure. The failure rate at 6 months will be estimated from the Kaplan-Meier curve, and the rate and 95% confidence interval will be reported.

Time to non-relapse mortality will be computed as study enrollment to non-relapse death. Cumulative incidence methods will be used to estimate the distribution with relapses and relapse related deaths as competing events. The rate at 6 months will be estimated from the curve along with 95% confidence intervals.

For subjects treated on the extension study, the response rate at 12 months will be reported as a proportion and 95% exact confidence interval.

For subjects on steroids at baseline, we will explore the change in dose of steroids at 6 months. We will calculate the average percent change in dose for each subject along with a 95% CI. We will also determine the number and proportion of subjects that had a dose reduction greater than 50% as well as an exact 95% confidence interval.

10.2.3 Safety endpoint

Safety endpoints will be assessed on the safety analysis set. All adverse events recorded during the study will be summarized by each subject. The incidence of treatment-emergent adverse events (new or worsening from baseline) will be summarized by severity and type of adverse event. Listings of deaths, severe adverse events, and adverse events leading to early termination of study treatment or premature withdrawal from study will also be provided.

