5.1 Treatment Schedule and Administration: Ruxolitinib

Drug	Dose/Frequency	Duration	Administration
Ruxolitinib	10 mg BID	6 months, may extend up to 12 months	Oral

Subjects will receive oral ruxolitinib at a dose of 10 mg twice daily. Doses may not exceed 10 mg twice daily. Subjects will record their intake on a medication diary provided to them. Ruxolitinib will be continued for 6 months, unless there is intolerable toxicity, chronic GVHD progression requiring additional systemic treatment or relapse of the underlying malignancy. Subjects with mixed responses or chronic GVHD progression prior to 6 months of therapy that does not require initiation of additional agent are allowed to continue ruxolitinib for the complete 6 month duration. Therapy duration of 6 months will ensure adequate exposure to ruxolitinib, and is important because of the limited options for therapy in the study population and limitations of the current response assessment.

Extended treatment

Subjects who continue to have stable disease, mixed responses or partial/complete responses at the end of 6 months may continue the drug for a total of 12 months. Subjects with chronic GVHD progression (not including stable disease or mixed responses) at the end of 6 months will stop ruxolitinib, regardless of whether or not a new systemic therapy has been added.

Ruxolitinib taper prior to discontinuation

At the end of 6 months, or 12 months for subjects treated on extension study, ruxolitinib will be tapered over a month before discontinuation, for example, a dose reduction by 5 mg every 1-2 weeks. Ruxolitinib may be stopped without a taper in cases of unacceptable toxicities. If an UNMC IRB # 333-18, Protocol Version 1.6 dated 25Jan2021

abrupt cessation of ruxolitinib is required, investigators are strongly encouraged to consider starting or dose-escalating systemic glucocorticoid (prednisone dose ≥ 0.5 mg/kg/day or equivalent dose) for at least a week to avoid rebound symptoms. While coming off ruxolitinib, subjects should be carefully monitored for worsening of GVHD symptoms or any other withdrawal symptoms.

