5.4 Duration of Study and Follow-up

We estimate that there will be 47 subjects dosed over a 2.5-year period. After accrual is met, we plan to follow the subjects for up to 2 years; the follow-up duration is discussed in detail in the table below.

GVHD response evaluation every 3 months	Therapy duration	End of therapy safety evaluation (30-40 days after the last dose of the study drug)	Last follow-up for GVHD evaluation	Data collection
Stable disease or mixed responses at the end of 6 months	6 to 12 months followed by taper over 1 month ¹	8 months; If therapy continued till 12 months and tapered over the next month, 14 months ²	At the end of 6 months; If therapy continued until 12 months, up to 24 months from the study enrollment ³	Data on survival, relapse of malignancy, subsequent GVHD treatment will be collected till subjects are removed from the study, death or up to a total of 2 years. For subjects who have completed last follow-up for GVHD evaluation, further data may be collected via review of medical records or telephone interview.
Partial/complete responses at the end of 6 months	6 to 12 months followed by taper over 1 month ¹	8 months ⁴ ; If therapy continued till 12 months and tapered over the next month, 14 months ²	Up to 24 months from the study enrollment ³	
GVHD progression, toxicity or relapse ⁵	<6 months (may stop without a taper)	About 30 days after the last dose	At the end of 6 months	

¹If no intolerable toxicity, chronic GVHD requiring initiation of an additional systemic agent, or relapse of underlying malignancy within the 6 months of the study participation, ruxolitinib may be continued till 12 months

²If no toxicity concerns were raised at 12-month follow-up, this evaluation may be performed over the phone with a plan to see the subject in a follow-up at 15 months.

³The subject will be followed every 3 months until progression of chronic GVHD requiring initiation of an additional systemic agent, relapse of underlying malignancy or for a total of 2 years

⁴For subjects with partial or complete responses at 6 months, if no toxicity concerns were raised at 6-month follow-up, this evaluation may be performed over the phone with a plan to see the subject in a follow-up at 9 months.

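### Adverse-event incidence is pooled over subject-specific windows of about 1 to about 14 months, with no exposure summary and no 6-month figure

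*Combined protocol and SAP*

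**What the plan says.** - **Who counts.** Section 10.1: "If a subject receives one dose of ruxolitinib then the subject will be included in the safety analysis set". There is no minimum exposure, and "the study will dose 47 subjects".
- **What is reported.** Section 10.2.3 takes in all adverse events recorded during the study and plans one summary: "The incidence of treatment-emergent adverse events (new or worsening from baseline) will be summarized by severity and type". It names no time window, person-time, split between the first 6 months and the extension, or exposure summary. No other section supplies one.
- **How long subjects are treated.** The Section 5.1 table gives "6 months, may extend up to 12 months". At either stopping point "ruxolitinib will be tapered over a month before discontinuation". The Section 5.4 table repeats this as "6 to 12 months followed by taper over 1 month" and has a separate row for treatment shorter than 6 months, which may end without a taper.
- **Who gets the longer treatment.** Section 5.1: "Subjects who continue to have stable disease, mixed responses or partial/complete responses at the end of 6 months may continue the drug". Note 1 to the Section 5.4 table adds that there must have been no intolerable toxicity, no chronic GVHD needing a further systemic agent and no relapse in the first 6 months. Section 5.1 has subjects with progression at month 6 stop.
- **How long events are collected.** Section 9.2.2 sets the period from consent to 30 days after the final dose.

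**The concern.** The chance of at least one event of a given type grows with time under observation. When that time differs several-fold between subjects, a single percentage over all dosed subjects mixes risks over different periods, and the mixture depends on how many subjects extend. Extension is also not random: it is open to those who tolerated the drug and did not progress, so the longest windows belong to a selected group.

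What is at stake is how the safety table reads. Someone weighing response at 6 months against harm needs the adverse-event risk over the same 6 months. Section 10.2.1 fixes that time point for response, treatment failure and non-relapse mortality, and reports 12-month response separately for extension subjects. Adverse events get no such time point.

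**Working it through.** The plan states no adverse-event rate or exposure total, so there is no figure of its own to reproduce.

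**Step 1. Length of the collection window, from first dose** (Sections 5.1, 5.4 and 9.2.2; 30 days taken as 1 month)

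| Course | On drug | Window |
|---|---|---|
| Stops after the first doses | close to 0 | about 1 month |
| Stops before month 6, no taper | under 6 months | under 7 months |
| 6 months, then taper | 6 + 1 = 7 months | 7 + 1 = 8 months |
| 12 months, then taper | 12 + 1 = 13 months | 13 + 1 = 14 months |

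The Section 5.4 table places the safety evaluations at months 8 and 14, which confirms the last two rows. The extended course is 13/7 = 1.9 times the 6-month course in time on drug.

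**Step 2. Effect on the pooled percentage.** The documents give neither event hazards nor an expected extension share, so these are assumptions: constant hazard, 30% with a given event by 6 months, the same hazard in extenders and non-extenders, and no early stoppers.

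Risk over t months = 1 − 0.70^(t/6).

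- 8 months: 1 − 0.70^(8/6) = 1 − 0.622 = 0.378
- 14 months: 1 − 0.70^(14/6) = 1 − 0.435 = 0.565

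Pooled incidence with share f extending = (1 − f) × 0.378 + f × 0.565.

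| f | Pooled incidence | 6-month risk |
|---|---|---|
| 0 | 38% | 30% |
| 0.30 | 43% | 30% |
| 0.50 | 47% | 30% |
| 0.70 | 51% | 30% |

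Even with no one extending, the pooled figure exceeds the 6-month risk, because the taper and the 30-day follow-up count.

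**Step 3. With early stoppers.** Assume windows of 4, 8 and 14 months and a hazard of 0.05 per month. The risk over t months is 1 − exp(−0.05t): 18.1%, 33.0% and 50.3% for the three windows, and 25.9% by 6 months.

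| Early / 6-month / extended | Pooled incidence |
|---|---|
| 50% / 30% / 20% | 29.0% |
| 30% / 30% / 40% | 35.5% |
| 20% / 20% / 60% | 40.4% |

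The underlying 6-month risk (25.9%) and the person-time rate (5 per 100 person-months) are the same in every row. The share of early stoppers changes along with the extended share here, so the spread reflects both. At 0.02 per month the first and last rows give 13.2% and 19.1% against a 6-month risk of 11.3%. At 0.10 they give 48.1% and 62.8% against 45.1%.

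**The case against.** The case against giving this much weight is substantial.

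- **A period is defined.** A reader might infer that the percentages refer to no defined exposure at all. The documents do not support that: first dose to 30 days after the last dose is an ordinary on-treatment window. It differs by subject, which is a narrower complaint. That the incidence will be a simple percentage of dosed subjects is likewise an inference, although no other denominator is given.
- **Comparison with other ruxolitinib data.** A reader might infer that the results could not be set beside existing data. Most of the figures the protocol quotes are themselves percentages over variable exposure: median exposure of 10.8 months in the myelofibrosis trials and 7.8 months in the polycythemia vera trial, and median follow-up of 22 weeks (range 3–135) in the retrospective GVHD series. Section 8.1.10 lists percentages alone. What remains is that the Introduction gives the trial percentages with their exposure, while this plan provides for no exposure summary of its own.
- **Size.** The hazard and the 30% are assumed. If subjects who extend are those who tolerate the drug, their later risk may be lower and the inflation smaller. Early stoppers also lower the pooled figure. With 47 subjects, the 95% half-width at 40% incidence is 1.96 × √(0.4 × 0.6/47) = 14 points, wider than the 8-point difference between 30% and 70% extending. That limits the practical size. It does not remove the mismatch in time point, which is systematic.
- **No decision rests on the table.** The trial has one arm, safety is not among the objectives in Section 1, and mortality has its own boundary in Section 10.4. The monitoring committee receives all serious and grade 3 or higher events. This stands in full.
- **It can be done at reporting.** True, since the dates will exist. Stating it beforehand costs little and avoids choosing the presentation after the results are seen.

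**Conclusion.** The point holds as a gap in descriptive safety reporting. Followed as written, Section 10.2.3 yields a percentage over windows of about 1 to about 14 months. Their length depends on 6-month outcome, no exposure summary accompanies the figure, and nothing gives the risk over the 6 months used for efficacy. Under the assumptions in Step 2, a fixed 30% 6-month risk appears as anything from about 38% to 51% as the extending share goes from none to 70%. Early stoppers or a lower risk among extenders would reduce these values. The direction follows from the design; the size is illustrative.

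It would be tempting to read this as biasing the trial's conclusion or its safety stopping. It does neither: there is no between-group contrast, and the primary endpoint, the sample size and the mortality boundary do not use this table. It is an inexpensive improvement that should be made.

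**What to change.** In Section 10.2.3 keep the overall incidence and add:

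1. a summary of exposure duration: median, range and total patient-time;
2. incidence in the first 6 months from day 1, for the whole safety set;
3. incidence after month 6 through 30 days after the last dose, for all subjects still under collection, shown separately for extension subjects and for those who taper at month 6, so that events in months 6 to 8 among non-extenders are not lost;
4. events per patient-year for grade 3 or higher events, infections and cytopenias.

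For item 2, say how subjects whose collection ends before month 6 are handled. A simple proportion still counts them over a shorter window. With the Step 3 inputs it would be 0.50 × 18.1% + 0.50 × 25.9% = 22.0% with half stopping early, and 0.20 × 18.1% + 0.80 × 25.9% = 24.3% with a fifth, against a 6-month risk of 25.9%. That is a much smaller movement than in the pooled figure.

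The cost is a few more table columns. Event and last-dose dates are already needed to apply the 30-day limit, and dosing diaries and accountability records are already required, so no visit or sample is added. Cells after month 6 will be sparse with at most 47 subjects, and person-time rates are easiest to read when the hazard is roughly constant, which is why they accompany the 6-month incidence and do not replace it.
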